## 5.7 Subject Completion/Early Withdrawal

It will be documented whether or not each subject completed the clinical study. A subject is considered to have completed the study if he/she has taken all study medications for 6 months and has completed 6 month study assessments or withdrew from the study due to the occurrence of a recurrent embolic stroke, hemorrhagic transformation or death. If a subject does not complete the treatment phase, their data will be used for efficacy and for any safety analysis.

It is understood that withdrawals may occur during a trial. Each subject has the right to withdraw from the trial at any time for any reason without affecting the right to treatment by the investigator. Subjects who do not complete the treatment phase for other reasons then mentioned above, should be followed at day 14 and EOS visits, if possible. At minimum these patients should have a monthly phone call to assess AE/SAE and vital status if they are unable to continue follow-up in clinic.

Subjects needing to withdraw prior to the completion of the study and who do not agree to continue in follow-up should return to the clinic for completion of early withdrawal procedures, as outlined in table 1.

Reasons that a subject may discontinue the study include the following:

- Adverse events including recurrent stroke or hemorrhagic transformation
- Intercurrent illnesses
- Any significant new medical condition
- Protocol violation
- Non-compliance to study medication regimen

- Use of any investigational drug other than the study medication
- Intake of prohibited medication
- Pregnancy
- Subject withdrew consent or lost to follow-up
- Other (reason to be documented)

Withdrawals due to intercurrent illnesses or AEs will be fully documented in the CRF with the addition of supplementary information if available and/or appropriate. Withdrawals due to non-attendance will be followed-up by the investigator to obtain the reason for non-attendance.

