#### **8.1.2 Efficacy Analysis/Primary Aim**

For the main outcomes, the proportion of patients with any primary outcome (fatal stroke, recurrent ischemic stroke, transient ischemic attack) will be computed along with the 95% confidence interval for the differences in treatment arms.

The primary outcome is defined as any component of the composite primary outcome occurred within 30 and 180 days or otherwise had adequate follow-up. Logistic regression models will be fitted with the primary outcome as the dependent variable and the SUBGROUP: (1) Apixaban TIA: day 0-3; (2). Apixaban small stroke: day 3-5; (3). Apixaban medium stroke: day 7-9; (4) warfarin TIA: day 7±5; (5) warfarin small stroke: day 14±5; (6) warfarin medium stroke: day 14±5 as the primary independent variable. The overall treatment effect will be assessed by the ESTIMATE and LSMEANS of all the Apixaban groups to all the warfarin groups. Comparison between individual subgroups will be assessed by constructing different ESTIMATE. For example, (1) Apixaban TIA versus (5) warfarin Small stroke: day 14±5. These analyses will be implemented by using SAS 9.2 PROC LOGISTIC which has the ESTIMATE and the LSMEANS statements for the group comparisons. P<0.05 is used for the overall treatment effects. All other subsequent subgroup testing will be adjusted for multiple comparisons by using PROC PLM.

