**8.1.4 Potential Confounders**

Age and sex as well as a variety of clinical variables (e.g. CHADS2-VASc, CHA2DS2) that are risk factors for embolic stroke, and their associations with fatal or recurrent embolic stroke or hemorrhagic cerebral bleed will be examined. Other clinically relevant variables that are shown to differ between treatment regimens at enrollment will also be examined as potential confounders.

For missing data, both an intent-to-treat analysis (in which subjects are analyzed according to their randomized assignment) and a per-protocol analysis (in which subjects not treated according to their randomized assignment and/or with other major protocol violations are removed from this analysis) will be conducted. Sensitivity analyses to assess the effect of missing outcome data on the primary result will be conducted

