**8.1.5 Sample Size and Power**

As a pilot, open-label study, this project is intended to generate data to be used in the development of future, larger studies. A total of 120 patients are expected to be available and eligible to participate in this study and up to 125 may be screened in order to yield 120 randomized participants.

Review of our database indicates the risk of fatal or recurrent stroke in patients with atrial fibrillation is approximately 20% with standard treatment . To calculate expected power in this study, this established risk was used as the basis for estimates that could be expected with this treatment if it is successful. Given the parameters of conducting a 2-sided test with alpha = .05, and equal allocation to treatment and control groups (50 patients per group), power calculations were conducted using various ratios of outcomes (i.e. fatal or recurrent stroke) in the control group compared to the experimental group. The following results were obtained:

Power	Detectable outcome Risk in control / Risk in experimental
80% power	2.30

90% power	2.52
99% power	3.00

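### The primary outcome rule makes evaluability depend on an undefined follow-up standard, so event-free dropouts probably leave the denominator and their partial follow-up is lost

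*Combined protocol and SAP*

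**What the plan says.** - **Outcome rule (8.1.2).** The primary outcome is "any component of the composite primary outcome occurred within 30 and 180 days or otherwise had adequate follow-up". No section says what makes follow-up adequate at day 30 or day 180.
- **Model (8.1.2).** The plan reports "the proportion of patients with any primary outcome" with a 95% confidence interval for the difference between arms, and "Logistic regression models will be fitted with the primary outcome as the dependent variable". No time-to-event method or censoring rule is given.
- **Non-completers (5.7).** "If a subject does not complete the treatment phase, their data will be used for efficacy and for any safety analysis". Patients who stop treatment are to be seen at day 14 and end of study if possible, with at least monthly calls if they cannot attend. Patients who refuse further follow-up have an early withdrawal visit. A patient who withdraws because of a recurrent embolic stroke, haemorrhagic transformation or death is classed as having completed; one who withdraws event-free is not.
- **Missing data (8.1.4).** The paragraph opens "For missing data, both an intent-to-treat analysis", adds a per-protocol analysis, and then promises sensitivity analyses for missing outcome data. It names no method for them.
- **Safety outcome (8.1.3).** Intracranial haemorrhage is to be coded 0 or 1 for everyone at both time points. How an unknown value is coded is not stated.

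**The concern.** Read literally, the 8.1.2 sentence would make adequate follow-up an outcome in itself, which cannot be meant. The workable reading is an evaluability rule: a patient is analysed if an event occurred, or, failing that, if follow-up was adequate. Whether a patient is analysed then depends on the outcome. Someone who has an event in week two and then leaves stays in; someone who leaves in week two without an event drops out of numerator and denominator alike. A logistic model needs a 0 or 1, so the event-free time of the second patient is not used at all.

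Because the standard is undefined, the analyst must choose it, possibly with the data in view. The final visit has a window of ±10 days, so it is unclear whether a patient last seen event-free on day 170 counts. A death from a non-stroke cause on day 60 is not placed either.

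Two things are at stake. Section 8.1.5 says the pilot is meant to supply data for larger studies, so the absolute risks matter. And in an open-label comparison, unequal dropout would carry over into the treatment difference.

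**Working it through.** **Inputs**

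- Control risk: 8.1.5 says the risk "is approximately 20% with standard treatment". Taken as the true 180-day risk, p = 0.20.
- Arm size: 120 patients at 1:1 (4.1), so 60 per arm. Test: "conducting a 2-sided test with alpha = .05".
- Dropout, d: no rate is given. The only allowance is in 4.2.2, where up to 125 patients cover drop-outs and screen failures together: 5/125 = 4%. Rates of 5%, 10% and 20% are assumptions.

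The plan offers no figure for dropout or its effect, so there is none to reproduce. The power table in 8.1.5 does not enter this check.

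**Step 1. Reported risk under the evaluability reading**

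Let E be the observed events and C the event-free patients with full follow-up, both as fractions of those randomised. Reported risk = E / (E + C), with C = (1 − p)(1 − d).

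- Upper figure, all events precede dropout: E = p.
- Lower figure, constant event and dropout hazards: E = [ln(1 − p) / (ln(1 − p) + ln(1 − d))] × [1 − (1 − p)(1 − d)].

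Example at d = 20%: C = 0.80 × 0.80 = 0.64. Upper: 0.20/0.84 = 23.8%. Lower: the two hazards are equal, so E = 0.5 × 0.36 = 0.18 and 0.18/0.82 = 22.0%.

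| d | E (constant hazards) | C | Lower | Upper | Dropouts coded 0 (constant hazards) |
|---|---|---|---|---|---|
| 4% | 0.196 | 0.768 | 20.3% | 20.7% | 19.6% |
| 5% | 0.195 | 0.760 | 20.4% | 20.8% | 19.5% |
| 10% | 0.190 | 0.720 | 20.9% | 21.7% | 19.0% |
| 20% | 0.180 | 0.640 | 22.0% | 23.8% | 18.0% |

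The last column is the other coding that the text leaves open. At 20% dropout and constant hazards, an unwritten choice moves the reported risk between 18.0% and 22.0%.

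At a true risk of 10%, the same formulas give 10.5–11.0% at 10% dropout and 11.1–12.2% at 20%.

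**Step 2. When the bias is upward**

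Let D be the event-free dropouts and q their risk after leaving. True risk = [(E + C) × reported risk + D × q] / (E + C + D), a weighted average of the reported risk and q. So the reported risk is too high only if q is below it, correct if they are equal, and too low if q is higher. In the 20% constant-hazard example, D = 1 − 0.18 − 0.64 = 0.18 and q = (0.20 − 0.18)/0.18 = 11.1%, below 22.0%.

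**Step 3. Effect on the comparison when there is no true effect (20% in both arms)**

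- Equal dropout: the odds ratio is 1.00.
- Apixaban 5%, warfarin 20%, constant hazards: 20.43% versus 21.95%, difference −1.5 points, odds ratio (0.2043/0.7957)/(0.2195/0.7805) = 0.91.
- Same rates, all events first: 20.83% versus 23.81%, difference −3.0 points, odds ratio 0.80/0.95 = 0.84.
- Swapping the rates gives the reciprocals, 1.10 and 1.19.

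Simulated two-sided type I error with 60 per arm and all events before dropout is about 5.0% at 5%/5%, 5.8% at 5%/15% and 6.8% at 5%/20%.

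**Step 4. Against sampling error**

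The 95% half-width for the risk difference is 1.96 × √(2 × 0.20 × 0.80/60) = 14.3 points.

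**The case against.** The strongest reply is that the plan nowhere says event-free dropouts are removed. That is inferred from a badly built sentence, while other sections pull the other way: 5.7 keeps patients under observation after they stop treatment, 7.5.2 requires monthly follow-up after dosing is suspended, and 8.1.4 promises analysis by assigned arm plus missing-outcome sensitivity analyses. This stands as far as it goes. These provisions should reduce missing outcomes, but none states who is in the primary denominator, and the sensitivity analyses have no defined primary rule to vary.

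A reader might infer four stronger things that the documents do not support:

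- **That the reported risks are shown to be inflated.** Step 2 makes this conditional on the dropouts' later risk, and at the 4% allowance the effect is under 1 point.
- **That 8.1.2 contradicts 5.7.** The 5.7 sentence concerns patients who do not complete treatment, not patients whose outcome is unknown. The two can coexist.
- **That the warfarin arm will lose more patients because it has more scheduled visits.** The scheduled visits are the same in both arms, with INRs drawn at them. Only the unscheduled INR returns (5.2, 5.6.1) are extra. Unequal dropout is possible in an open-label trial with different start times, but the documents do not establish its direction.
- **That the plan ignores missing outcomes.** It promises sensitivity analyses; what it lacks is the method.

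It is also fair that even the −3.0 points in Step 3 are small beside a half-width of 14.3. But that bias does not shrink with sample size, and it would pass into the planning of a larger trial. Finally, time-to-event methods are not a plain substitution. Section 7.1 includes new haemorrhagic stroke, which 2.3.2.2 extends to asymptomatic imaging findings, and follow-up imaging is scheduled only at day 14 and end of study. Such events have no exact onset date, so the fix needs a dating rule.

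**Conclusion.** The point holds as a defect in the primary outcome definition, not as demonstrated bias. On the only workable reading, inclusion depends on the outcome through an undefined term, the logistic model discards partial follow-up, and no other section repairs the denominator.

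The size depends on dropout, which the documents do not give. With a true risk of 20% and dropout unrelated to risk, inflation is 0.3–0.7 points at 4% dropout, 0.9–1.7 at 10% and 2.0–3.8 at 20%. The comparison is disturbed only by unequal dropout. It merits correction before outcome data are examined because the change is cheap and removes a choice that could otherwise be made after the results are seen.

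**What to change.** In 8.1.2, delete the adequate follow-up phrase and state instead:

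1. All randomised patients are analysed by assigned arm.
2. Risk at 30 and at 180 days from randomisation is estimated by Kaplan-Meier, or by cumulative incidence with non-stroke death as a competing event. The latter is preferable if such deaths occur. Event-free patients are censored at last contact.
3. The estimate is stratified by stroke type and reported as a risk difference with 95% CI. Strata should be weighted by size, since some may have no events.
4. An event found only on scheduled imaging is dated at the scan. The text should also say how a final scan taken after day 180 but within the ±10-day window is counted.

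Keep the logistic model as supportive. In 8.1.4, separate the analysis sets from missing-data handling, and specify the promised sensitivity analyses as multiple imputation of missing outcomes and a tipping-point check.

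**Cost.** Revised SAP wording, modest programming, and a check that event and last-contact dates are captured; the scheduled visits and monthly calls should supply them. The price is an assumption of non-informative censoring, which the tipping-point check probes, and approximate timing for imaging-only events.

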**5.2 Baseline Visit/Randomization**

The baseline/randomization visit will be performed up to 48 hours after signs and symptoms of stroke or TIA, and will be combined with the screening visit as long as all inclusion/exclusion criteria have met prior to randomization.

After subjects have been screened and enrolled in the study, baseline assessments will be performed. Patients will be stratified according to their type of stroke ( TIA, small or medium stroke) and randomized 1:1 in each group to ensure for equal number of subjects for each three types. Treatment with APIXABAN 5mg or 2.5mg based on clinical characteristics defined in section 1.4 or Warfarin ( target INR 2-3) will begin based on the randomization treatment regimen. Study treatment regimen is initiated based off of TIA or stroke size. Subjects in the Warfarin arm will return to clinic with unscheduled INR checks until they reached the standard INR of 2.0 to 3.0.

Hypertension will be treated per the AHA/ASA guidelines and are described below:

Goals for target blood pressure level or reduction from pretreatment baseline are uncertain and should be individualized, but it is reasonable to achieve a systolic pressure less than 140 mm Hg and a diastolic pressure less than 90 mm Hg. For patients with a recent lacunar stroke, it might be reasonable to target a systolic blood pressure of less than 130 mm Hg.

Resumption of Blood Pressure therapy is indicated for previously treated patients with hypertension.

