### 8.1.6 Randomization

Randomization of treatment was calculated in SAS 9.4 using a stratified, blocked PLAN procedure. For the 120 subjects to be randomized to either apixaban or warfarin, a random seed number was generated. Each subgroup of stroke type (small stroke, medium stroke and TIA) was randomized implementing block randomization using four blocks of 10. The treatment allocation was created by an unblinded statistician and given to the TGH research pharmacy. Blinded study envelopes are provided to study team members for randomization.

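### The overall P<0.05 test is a six-cell log-odds contrast with no provision for zero-event cells; at 20% vs 8.7% risk its power is about 14%, against 42% for a stratified test.

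*Combined protocol and SAP*

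**What the plan says.** Section 8.1.2 (Efficacy Analysis/Primary Aim) begins with the proportion of patients who have a primary outcome, which "will be computed along with the 95% confidence interval for the differences in treatment arms". No test is attached to that interval. The section then states: "Logistic regression models will be fitted with the primary outcome as the dependent variable and the SUBGROUP" as the primary independent variable. SUBGROUP has six levels, apixaban or warfarin crossed with TIA, small stroke or medium stroke.

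The significance test comes from this model: "The overall treatment effect will be assessed by the ESTIMATE and LSMEANS of all the Apixaban groups to all the warfarin groups", and "P<0.05 is used for the overall treatment effects". Comparisons between individual subgroups use further contrasts, illustrated by: "For example, (1) Apixaban TIA versus (5) warfarin Small stroke: day 14±5".

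Cell sizes follow from the randomisation. Section 5.2 has patients stratified by event type and "randomized 1:1 in each group to ensure for equal number of subjects for each three types". Section 8.1.6 specifies, for each stroke type, "block randomization using four blocks of 10". Section 8.1.3 takes over much the same analysis for intracranial hemorrhage, with one-sided tests.

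No section covers an outcome cell without events. Fisher's exact test is named only for baseline variables (8.1.1), and the sensitivity analyses in 8.1.4 concern missing data.

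**The concern.** A logistic model with one six-level factor is saturated: each cell's log-odds is estimated from that cell alone. The overall contrast adds three such log-odds and subtracts three others. If one cell has no events, its estimate runs off to minus infinity, its standard error grows without bound, and the Wald statistic for the whole contrast collapses towards zero.

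This happens mainly when apixaban does well, since low risk is what empties a cell. The trial could then show a clear difference in proportions while its stated P<0.05 test reports nothing. The overall question does not need six separate log-odds. The subgroups are of stated interest (sections 3.2 and 3.3), but they can be examined in a separate model.

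The example contrast has a different fault. It compares apixaban after TIA with warfarin after small stroke. These patients come from different randomisation strata, so drug and stroke type are confounded.

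**Working it through.** **Inputs.** Total 120 (4.2.2); three strata, 1:1 (5.2); four blocks of 10 per stroke type (8.1.6), so 40 per stratum and 20 per cell. Two-sided alpha 0.05 (8.1.5). Section 8.1.5 says "the risk of fatal or recurrent stroke in patients with atrial fibrillation is approximately 20% with standard treatment", while section 1.2 says about 25%. The risk ratio is 2.30, the 80% power row of 8.1.5, so apixaban risk = 0.20/2.30 = 8.7%. Equal risk in the three strata is an assumption, because the documents give no stratum-specific risks.

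**The plan's own power figure.** With n = 50 per arm, mean risk p̄ and the pooled normal formula, power = Φ[(|p1−p2| − 1.96·√(2p̄(1−p̄)/n)) / √((p1(1−p1)+p2(1−p2))/n)].
- 20% vs 8.7%: Φ[(0.1130 − 0.1374)/0.0692] = 36%, not 80%.
- 46% vs 20%: Φ[(0.26 − 0.1843)/0.0904] = 79.9%. The other two rows (90.1% and 99.0%) also reproduce when 20% is the lower of the two risks.

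The table therefore does not match its stated control risk. That is a separate matter, but it is why both sets of rates are carried below.

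**Probability of an empty cell** (exact, 20 per cell, 20% vs 8.7%).
- One warfarin cell: 0.8^20 = 0.0115. At least one of three: 1 − (1−0.0115)^3 = 3.4%.
- One apixaban cell: 0.913^20 = 0.162. At least one of three: 1 − (1−0.162)^3 = 41.2%.
- Any of six: 1 − 0.966 × 0.588 = 43.2%.

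**Power at 20% vs 8.7%** (200,000 simulated trials, mean 17.2 events).
- Six-cell Wald contrast: 23.7% without an empty cell, 0% with one, so 0.568 × 0.237 = 13.5% overall. Stopping the fitting after 5, 8 or 12 iterations does not change this. Of about 2,580 fitted empty-cell trials, none rejected.
- CMH stratified by stroke type, no continuity correction: 41.9% overall, 59.5% in empty-cell trials. Without an empty cell: (0.419 − 0.432 × 0.595)/0.568 = about 29%.
- Logistic model with treatment plus stratum (6,000 trials): 40.2%.
- Six-cell contrast with 0.5 added to events and non-events in each cell (Firth-type): 31.2%.

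Empty-cell trials account for 0.432 × 0.595 = 0.257 of the 0.419 − 0.135 = 0.284 gap. Without an empty cell the contrast still loses a little (24% against 29%).

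The large-sample formula hides this. The summed log-odds difference is 3 × 0.965 = 2.895 and its standard error 1.681, so z = 1.72 and nominal power is 41%.

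**Sensitivity**

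| Control vs apixaban | Empty cell | Six-cell Wald | CMH |
|---|---|---|---|
| 20% vs 8.7% (8.1.5) | 43% | 14% | 42% |
| 25% vs 10.9% (1.2) | 28% | 29% | 53% |
| 30% vs 13.0% (assumed; the 8.1.2 composite adds TIA) | 17% | 46% | 63% |
| 46% vs 20% (reproduces the power table) | 3% | 84% | 87% |

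With 17 per cell (50/3, the arm size used in 8.1.5) at 20% vs 8.7%, the three figures are 55%, 7% and 37%. With stratum control risks of 10/20/30%, or cells of 10/20/30 patients, the planned contrast falls to 7% and CMH stays at 42–44%.

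**Type I error** at 20% in both arms: six-cell contrast 3.4%, CMH 4.9%. CMH does not gain its power by being liberal.

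**Hemorrhage (8.1.3).** The documents give no rate. With an assumed common risk p, P(empty cell) = 1 − (1−(1−p)^20)^6 = 93%, 54%, 21% and 7% at p = 5%, 10%, 15% and 20%.

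**The case against.** The strongest points against are these.

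- **The collapse is a Wald property.** Section 8.1.2 names no test statistic. A likelihood-ratio test of the same contrast stays finite, with about 48% power overall and 74% in empty-cell trials. This stands as a condition on the 14%. But ESTIMATE and LSMEANS output is most naturally read as Wald, and the likelihood-ratio version has type I error of 7–8%, so it is no clean rescue.
- **The difference in proportions survives.** With an unstratified Wald interval (the plan names none), the 95% CI excludes zero in about 46% of trials at 20% vs 8.7%, and in 63% of empty-cell trials. So the effect estimate is not lost. Yet in 70% of the trials where that interval excludes zero, the plan's own P<0.05 test is not significant (48% at a 25% control risk). The same section would give two conflicting answers.
- **It is a pilot** (4.1, 8.1.5). This limits the consequence. But the primary objective is comparative, a significance test is specified, and the results are meant to inform larger trials.
- **The event rate is uncertain.** Added composite components could raise it, and the TIA stratum could lower it. This stands, and the full range is needed: at the highest rates the loss is only 3 points.
- **CMH is used without continuity correction.** With it, power is 33%, close to the 31% of the Firth-type contrast. The choice must be declared; the uncorrected test holds its level here.

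**Conclusion.** The concern holds and should be fixed. At the control risks the documents state, the planned overall test has about 14% power (20% control risk) or 29% (25%), against 42% and 53% for a stratified test. Most of the loss comes from trials with an empty cell, which occur in 43% and 28% of trials respectively.

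These figures assume about 20 patients per cell, equal risk across stroke types, a risk ratio of 2.30, Wald inference with empty-cell trials counted as not significant, and CMH without continuity correction. The unequal stratum risks and cell sizes examined make the planned contrast worse. Higher event rates make the problem fade. The hemorrhage figures rest wholly on assumed rates.

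Changing the test does not make the trial well powered. Even the better test has only 42–53% power at a 20–25% control risk.

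**What to change.** In sections 8.1.2 and 8.1.3:

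1. Base the overall test on a logistic model with treatment and stroke type (three levels) as main effects, or on a CMH test stratified by stroke type. Name one, and state whether a continuity correction applies.
2. Report the stratified risk difference with its 95% CI as the effect estimate.
3. Name Firth or exact methods for use when events are very few. Firth on the six-cell contrast alone is not enough, since it recovers only about 31%.
4. Put subgroup comparisons in a separate treatment-by-stratum model, comparing apixaban with warfarin within the same stroke type only. Delete the cross-stratum example.

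The cost is SAP wording and a few lines of SAS, settled before outcome data are seen, with no change to data collection or sample size. The downside is that the overall estimate assumes a common effect across strata, which the separate treatment-by-stratum model can check only with low power.

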## **11 STUDY ADMINISTRATION**

### **11.1 Treatment Assignment Methods**

Subjects will be randomized at a 1:1 ratio for each treatment arm.

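### Section 8.1.2's only worked subgroup contrast, apixaban TIA against warfarin small stroke, crosses the randomisation strata and so mixes index-event type with treatment

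*Combined protocol and SAP*

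**What the plan says.** Section 8.1.2 fits a logistic model whose main independent variable, SUBGROUP, has six levels: apixaban TIA (1), small stroke (2) and medium stroke (3), then the same three event types on warfarin, (4) to (6). The overall treatment effect contrasts all apixaban cells with all warfarin cells at P<0.05. Then: "Comparison between individual subgroups will be assessed by constructing different ESTIMATE". The only illustration is "For example, (1) Apixaban TIA versus (5) warfarin Small stroke: day 14±5". On multiplicity: "All other subsequent subgroup testing will be adjusted for multiple comparisons by using PROC PLM". No adjustment method and no list of contrasts is given.

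On randomisation, section 5.2 says: "Patients will be stratified according to their type of stroke ( TIA, small or medium stroke) and randomized 1:1 in each group". Section 8.1.6 says: "Each subgroup of stroke type (small stroke, medium stroke and TIA) was randomized implementing block randomization using four blocks of 10". Section 11.1 repeats the 1:1 ratio.

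Section 8.1.3 takes over the primary-aim analysis for intracranial hemorrhage in all six subgroups, changing the outcome and using one-sided tests.

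**The concern.** Randomisation makes the arms comparable within an event type. It does not make TIA patients comparable with stroke patients. By the protocol's own definitions (2.3.2.1 and 7.5.1), a TIA leaves no acute damage on imaging and a small stroke is an infarct under 1.5 cm. Cells (1) and (5) therefore differ in index event as well as in arm. They also differ in the comparator's schedule: the model lists "4) warfarin TIA: day 7±5; (5) warfarin small stroke: day 14±5", so cell (5) does not even carry the warfarin regimen that apixaban TIA patients could have been allocated.

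An analyst who follows the text literally would report a non-randomised difference as a treatment contrast. For hemorrhage under 8.1.3, the same pairing would set patients without an infarct on apixaban against patients with one on warfarin. If infarcts bleed more (an assumption; the documents give no figures by type), that would tend to hide harm. The three types have different initiation windows, so the within-type effects are what a pilot meant to inform larger studies most needs.

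**Working it through.** **Plan's own figure.** The documents state no figure for any subgroup contrast. The power table in 8.1.5 concerns the two-arm comparison; only its 20% risk is borrowed below.

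**Which pairs are randomised.** Six cells give 6 × 5 / 2 = 15 pairs.
- Across arms: 3 × 3 = 9 pairs. Three stay within a type, (1) v (4), (2) v (5) and (3) v (6), and are randomised. Six cross types, and the example is one of them.
- Within one arm: 3 + 3 = 6 pairs. These compare event types, not treatments.

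**What each contrast estimates.** Let a_t be the log odds of the outcome on warfarin for event type t, and d_t the treatment effect (log odds ratio) within type t.
- (1) v (5): (a_TIA + d_TIA) − a_small = d_TIA + (a_TIA − a_small).
- (1) v (4): (a_TIA + d_TIA) − a_TIA = d_TIA.
- Overall, with equal weights: the mean of (a_t + d_t) minus the mean of a_t = the mean of d_t. The a_t cancel.

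The bias in the example is a_TIA − a_small, which is zero only if the two types carry equal risk. Event type is fully determined by SUBGROUP, so it cannot be added as a separate covariate to remove the bias. The imbalance checks in 8.1.1 compare treatment with control overall and would not detect it.

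**Cell size.** Four blocks of 10 per type (8.1.6) is 40 patients. At 1:1 that is 20 per cell, and 3 × 40 = 120 agrees with the planned total.

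**Size of the bias (assumed risks).** Take d_TIA = 0. For small stroke, assume 20%, the standard-treatment risk of fatal or recurrent stroke in 8.1.5. That is a working value only: the database described in 1.2 covers small to medium stroke, and no TIA risk is documented. TIA risk is varied. Odds ratio = [p_TIA/(1 − p_TIA)] / [p_small/(1 − p_small)]. Rejection is by exact binomial enumeration of the two-sided Pearson chi-square test at an unadjusted 0.05, with 20 per cell.

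| TIA risk | Small-stroke risk | Risk difference (points) | Expected odds ratio | Rejection |
|---|---|---|---|---|
| 20% | 20% | 0 | 1.00 | 5.0% |
| 15% | 20% | −5 | 0.1765/0.25 = 0.71 | 6.9% |
| 10% | 20% | −10 | 0.1111/0.25 = 0.44 | 13.8% |
| 5% | 20% | −15 | 0.0526/0.25 = 0.21 | 29.2% |
| 5% | 25% | −20 | 0.0526/0.3333 = 0.16 | 44.4% |

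**Same check on the randomised contrast.** For (1) v (4) with no drug effect the expected odds ratio is 1 whatever the TIA risk. Rejection is 1.2%, 3.9%, 5.0% and 5.1% at a common risk of 5%, 10%, 20% and 25%.

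**The case against.** The strongest reply is that this is one illustration of syntax for secondary testing in a pilot. The main inference is the overall contrast, which averages the same three types in each arm. The text does not exclude the within-type pairs, and subgroup tests are to be multiplicity-adjusted. Most of this stands, and it sets the severity. It does not make the contrast valid. It is the only example given, its cell number, label and start day all agree (so it is not a one-digit slip for cell (4)), and the adjustment controls the error rate, not confounding.

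A reader might infer three stronger things that the documents do not support.
- *That the primary test is confounded.* It is not: the a_t terms cancel.
- *That all 15 pairs will be tested with a Bonferroni correction, costing the valid comparisons power.* The plan names neither the family nor the method. Even on that reading, at the 20% control risk and ratio 2.30 of 8.1.5 (20% v 8.7%) with 20 per cell, power is about 8.2% at 0.05/3 = 0.0167 and 2.6% at 0.05/15 = 0.0033 (normal approximation). The within-type tests have very little power either way.
- *That a spurious significant result is to be expected.* That depends on assumed TIA risks and on the threshold. At 0.0033, a TIA risk of 5% against 15% to 20% after small stroke gives rejection in only about 0.2% to 1.3% of trials. The estimate and its interval stay biased whatever the threshold.

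**Conclusion.** The point holds. The single subgroup contrast that 8.1.2 illustrates is not a randomised comparison under 5.2 and 8.1.6, and it estimates case mix plus treatment. This follows from the plan's own text and needs no assumed figures.

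The size does rest on assumptions. With no drug effect and 20% risk after small stroke, the expected odds ratio is 0.71, 0.44 or 0.21 for a TIA risk of 15%, 10% or 5%, and it returns to 1 only if the two types carry equal risk. The rejection rates are for unadjusted tests and would be lower after adjustment. The overall apixaban-versus-warfarin contrast is sound. The affected contrasts are secondary, so the severity is should-fix.

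**What to change.** In section 8.1.2, replace the example with the three within-type contrasts: (1) v (4), (2) v (5) and (3) v (6). State that the PROC PLM adjustment applies over those three, and name the method. Drop any cross-type or within-arm comparison, or label it non-randomised and descriptive and report it without p-values. State in 8.1.3 that the same three contrasts apply to intracranial hemorrhage.

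A treatment-by-stroke-type interaction test (2 degrees of freedom) is optional; with about 20 patients per cell it would have little power, and its absence is not an error.

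The cost is one paragraph of analysis text and a cross-reference. No patients, visits or data are added.
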